The Screening Phase assessments will be performed within 28 days prior to study treatment. Eligible subjects will have pathologically confirmed DLBCL, having received at least 1 prior therapy, with documented disease that is relapsed or refractory in subjects ineligible for HDT and transplant. For Phase 2, subjects must have pathologically confirmed de novo non-GCB DLBCL by Hans method testing using immunohistochemistry (IHC).

The Treatment Phase will extend from the first dose of study treatment until criteria for permanent discontinuation of ibrutinib or study treatment are met ([Section 9.2](#)), such as disease progression, unacceptable toxicity or 2 years after the last subject has been enrolled, whichever occurs first. During the Treatment Phase, efficacy evaluations will be performed every 3 cycles (28-day cycle) as specified in [Section 7.3](#).

The Follow-up Phase will begin once a subject discontinues ibrutinib treatment and will continue until death, lost to follow up, consent withdrawal, or study end, whichever occurs first.

- Subjects who discontinue for reasons other than disease progression (ie, for adverse event or Investigator decision) will complete an End-of-Treatment Visit (30 ± 3 days from the last dose of ibrutinib, lenalidomide or rituximab, whichever is later), and must continue to have disease evaluations (12 weeks ± 7 days). (See [Figure 1](#))
- Subjects who discontinue due to disease progression will complete an End-of-Treatment Visit and be followed for survival and subsequent anticancer therapy (12 weeks ± 7 days) until study ends. (See [Figure 1](#))

It is imperative that survival status be assessed and that the date of death is documented for each subject who has died. The study completion is defined as 3 years from the last study treatment, the time point that all subjects have exited the study for any reason, or study termination at the Sponsor's discretion, whichever occurs first.

A Dose Level Review Committee will evaluate safety data following the completion of each dose observation period of the Phase 1b portion. Members of this committee will include the

[figure not shown]
Sponsor (at a minimum: the Medical Monitor or designee, a Drug Safety representative and a Biostatistician) as well as participating Investigators/designee.

Table 3: Dosing Schedule

Agent	Phase 1b		Phase 2	
	Cycles 1-6	Cycles 7+	Cycles 1-6	Cycles 7+
Ibrutinib	560 mg PO daily		560 mg PO daily	

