5.3.1. Phase 1b

Ibrutinib and rituximab will be administered at set doses and lenalidomide will be administered according to the assigned dose level (Table 4).

5.3.2. Phase 2

Subjects will be treated with ibrutinib in combination with lenalidomide and rituximab per the table below. If determined to be safe and tolerated in the Phase 1b portion of the trial, the proposed dose of lenalidomide is 20 mg. Additional subjects may receive 25 mg lenalidomide as outlined.

Each cycle is 28 days in length. Missed doses of ibrutinib, lenalidomide, and rituximab will not be made up. Treatment will continue until disease progression or unacceptable toxicity.

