5.5.5. Dose Delay, Reduction or Discontinuation of Lenalidomide

In order to initiate a new cycle of therapy with lenalidomide, the subject must have an ANC $\geq 1,000/\mu\text{L}$ and a platelet count $\geq 50,000/\mu\text{L}$ and no lenalidomide related Grade ≥ 3 toxicity on Day 1. If these two criteria are not met, the entire cycle with all drugs is to be delayed and a repeat assessment is to be performed per the Investigator's decision. The initiation of lenalidomide should be delayed until the subject meets the above criteria at which time the subject will initiate drug without dose modification. The initiation of lenalidomide may occur on any day of the cycle, but missed doses must be omitted. Omitted doses should not be made up, and lenalidomide dosing must end no later than Day 21 of any given cycle. Once a cycle has initiated, if lenalidomide must be held for toxicity during dosing, except for an AE of rash, lenalidomide will not resume until Day 1 of the subsequent cycle, provided the subject meets the cycle initiation criteria above, with dose adjustments as per [Table 6](#).

Treatment with lenalidomide should be withheld for any unmanageable, potentially study drug-related non-hematological toxicity that is Grade 3 or higher in severity and any hematologic toxicity as described in [Table 6](#). In the event the subject is diagnosed with a thyroid condition or experiences a drop in creatinine clearance to $\leq 60 \text{ mL/min}$, refer to [Table 6](#) for further instructions.

Any other clinically important events where dose delays may be considered appropriate by the Investigator must be discussed with the Medical Monitor.

Lenalidomide may be withheld for a maximum of 28 consecutive days for toxicity. Lenalidomide treatment should be discontinued in the event of a lenalidomide related toxicity lasting more than 28 days, unless approved by the Medical Monitor.

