7.3.1. Radiographic Imaging

Pretreatment tumor assessment will be performed within 28 days before the first dose of study drug. Lesions that have been irradiated cannot be included in the tumor assessment unless unequivocal tumor progression has been documented in these lesions after radiation therapy. A CT scan (with contrast unless contraindicated) of the neck, chest, abdomen, and pelvis and any other disease sites and a positron emission tomography (PET) scan are required for the pretreatment tumor assessment. Thereafter, a PET scan is to be performed to confirm CR if the PET result was positive at Screening or may be performed at any time if clinically indicated. Information on extranodal involvement (eg, gastric or ocular disease) will also be obtained. Lesions in anatomical locations that are not well visualized by CT may be measured at baseline by MRI instead and should continue to be measured by MRI until disease progression.

In the case where CT with contrast is contraindicated, an alternative would be MRI of the abdomen and pelvis with contrast and CT of the chest and neck without contrast. In this case, neck nodes cannot be used as target lesions.

During treatment, CT/MRI scans will be done for tumor assessments within 7 days of Day 1 of Cycle 4 and Cycle 7 and then every 3 cycles up to Cycle 25, and then every 6 cycles thereafter, until PD or use of alternative anticancer therapy.

NOTE: PET/CT hybrid scanners may be used to acquire the required CT images only if the CT produced by the scanner is of diagnostic quality, adheres to the specified slice thickness/scan parameters, and includes the use of intravenous (IV) contrast. Additionally, the CT images must be separated from the PET data prior to submitting the data, and cannot be transmitted as fused CT/PET images.

If using a hybrid machine to acquire both PET and CT, the PET must be performed prior to the CT with IV contrast as to not compromise PET results.

If independent CT and PET scanners are used, and the subject is receiving both scans on the same day, the PET must be performed prior to the CT with IV contrast.

De-identified copies of all scans and radiology reports (including those from screening) must be provided to the Sponsor or designee (eg – central imaging vendor). At the Sponsor's discretion, the Sponsor or designee may conduct an independent review of the Investigator responses.

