8.4.1. Response Follow-Up

Subjects who discontinue the study treatment for reasons other than PD will be followed every 3 months (± 14 days) until PD or use of alternative anticancer therapies. During this period, CT/MRI and PET scans will be done per the Investigator's discretion.

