^j Must be done in accordance with Celgene Revlimid REMTM program (US Sites) or global Pregnancy Prevention Program (PPP) guidelines (Ex-US Sites) for females of childbearing potential (FCBP). Day 15 of each Cycle only applies if a subject's menstruation is irregular. Serum or urine depending on site standard method. If positive at Screening Visit, the subject is not eligible to enroll. See [Appendix 7](#) and [Appendix 8](#) for pregnancy testing frequency requirements.

^k T/B/NK cell count and biomarkers should be done at pre-dose on Day 1 of Cycles 1, 2, 3, at response evaluation (ie, Day 1 Cycles 4, 7, 10, 13, 16, 19, 22, 25, and then every 6 cycles thereafter) and EOT Visits.

^l **Phase 2 only:** Serum Ig will be taken pre-dose Day 1 Cycle 1. Samples will also be taken at all response evaluation visits (eg, Cycle 4, 7, 10, etc.) and EOT Visit.

^m **Phase 2 only:** PK samples will be drawn according to the schedule [Table 9](#). For subjects who must take strong or moderate CYP3A inhibitors while on treatment with ibrutinib, additional PK blood samples for evaluation of ibrutinib exposure is requested.

ⁿ Pretreatment tumor assessment should be performed within 28 days before the first dose. A CT scan (with contrast unless contraindicated) of the neck, chest, abdomen, and pelvis and any other disease sites and a PET or PET/CT scan are required for the pretreatment tumor assessment. Thereafter, a PET scan is to be performed to confirm CR if PET result was positive at Screening or may be performed at anytime if clinically indicated. During treatment, CT/MRI scans will be done for tumor assessments within 7 days prior to Day 1 of Cycle 4 and Cycle 7, then every 3 cycles up to Cycle 25, and then every 6 cycles thereafter, until PD or use of alternative anticancer therapy. In the event that CT contrast is contraindicated, MRI of the abdomen and pelvis with contrast and CT of the chest and neck may be performed as an alternative. Lesions in anatomical locations that are not well visualized by CT may be measured at baseline from MRI instead and should continue to be measured from MRI until disease progression. Follow the [Cheson 2007](#) (Phase 1b) [Appendix 5](#) and [Cheson 2014](#) (Phase 2) [Appendix 6](#).

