CR rate	
The ORR is defined as the rate of subjects who achieve a CR, according to the revised International Working Group Response Criteria for NHL (Cheson 2014), as assessed by the Investigator
	The same as for ORR
DOR	
Time from the date of the first documented response (CR or PR) to the first documented evidence of PD or death from any cause.
 
For subjects who have achieved an overall response but did not die or progress at the time of analysis, DOR will be censored on the date of the last adequate post-baseline disease assessment, or on the date of the first occurrence of response (CR or PR) if there is no disease assessment afterwards.
	
Analysis of DOR will be based on the subjects who have achieved a response (CR or PR) prior to initiation of the next line of anticancer therapy in the all-treated population enrolled in Phase 2. The median DOR and its 2-sided 95% CI will be obtained using the same method described for PFS.
 
Similar analysis for duration of CR, as defined as time from the date of the initial CR to the first documented evidence of PD or death from any cause, will be performed for all treated subjects who have achieved a response of CR prior to initiation of the next line of anticancer therapy in Phase 2.

PFS	
Time from the date of the first dose of study drug to confirmed PD or death from any cause, whichever occurred first.
 
For subjects without disease progression or death, PFS data will
	
Kaplan-Meier method based on the all-treated population by dose level enrolled in Phase 2. The median PFS and its 2-sided 95% CI will be provided. PFS at landmark time points (e.g., 3, 6, 9, 12 months from the first study drug dose date) will also be obtained by the Kaplan-Meier method; 95% CI for the landmark PFS rates will be calculated.

Statistical Analysis Plan

PCYC-1123-CA

20APR2020

Endpoint	Definition	Analysis Method

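### On-treatment scans follow cycle starts, which toxicity may delay, so 3-month PFS can be biased upward; imaging after stopping treatment is also inconsistently specified

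*Protocol*

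**What the plan says.** **Scan timing on treatment.** Protocol Section 7.3.1 ties imaging to cycles: "CT/MRI scans will be done for tumor assessments within 7 days of Day 1 of Cycle 4 and Cycle 7", then every three cycles to Cycle 25. Section 8.3.18 uses the same anchor and also allows a response evaluation at any time if the investigator sees a reason. Appendix 1 (footnote n) gives a narrower window, "within 7 days prior to Day 1 of Cycle 4 and Cycle 7", and Section 8.3.10 lists the first scan under Cycle 3, Days 22-28.

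**Cycle timing.** Section 5.3.2: "Each cycle is 28 days in length". Under Section 5.5.5, if the Day 1 neutrophil, platelet or lenalidomide-toxicity criteria are not met, "the entire cycle with all drugs is to be delayed". Lenalidomide may be held for up to 28 consecutive days, or longer if the Medical Monitor approves. The same section also says lenalidomide may begin on any day of the cycle, with missed doses omitted and dosing finished by Day 21.

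**Landmarks and censoring.** SAP Table 4 asks for "PFS at landmark time points (e.g., 3, 6, 9, 12 months from the first study drug dose date"). PFS and DOR are censored at the last tumor assessment (Protocol Sections 10.3.4.2 and 10.3.4.3; SAP Table 4). Neither document has a rule for late or missed scans.

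**After stopping for reasons other than progression.** Section 3.1 says these subjects "must continue to have disease evaluations", at 12 weeks ±7 days, without naming imaging. Section 9.2 has all subjects followed for progression. Section 8.4.1 sets follow-up every 3 months ±14 days and then says "During this period, CT/MRI and PET scans will be done per the" investigator's discretion. Appendix 1, footnote a, agrees with Section 8.4.1.

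**The concern.** Scans run on the cycle clock and landmarks on the calendar. If toxicity delays cycle starts, the two drift apart. A subject whose first scan slips past 3 months counts as progression-free at 3 months unless death or an unscheduled evaluation shows otherwise, so more toxicity could make early PFS look better.

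The trial has no control arm scanned on the same schedule. Its PFS would naturally be read against outside figures such as those in Protocol Table 2, so an artefact of scan timing would not cancel.

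After treatment stops for toxicity or another non-progression reason, the date of progression, and whether a subject is an event or censored, can depend on who happens to be scanned.

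**Working it through.** **The plan's own figure.** The plan states no event count, power or precision for PFS or DOR. Its only powered figure is the ORR rule of 27 or more responses in 49. The exact binomial gives P(X ≥ 27 | 49, 0.40) = 0.0231 and P(X ≥ 27 | 49, 0.60) = 0.802, consistent with the stated 0.025 ceiling and 80% power. It does not depend on the argument below.

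**Calendar** (days since first dose; one month = 30.4375 days)
- Cycle 4 Day 1: 3 × 28 = 84 days.
- First-scan window: 84 ± 7 = 77 to 91 under Section 7.3.1; about 77 to 84 under Section 8.3.10 and Appendix 1.
- 3-month landmark: 3 × 30.4375 = 91.3 days.
- Margin: 91.3 − 84 = 7.3 days for a scan at nominal Day 1; 91.3 − 77 = 14.3 days for the earliest permitted scan; 91.3 − 91 = 0.3 day at the late edge of the two-sided window.

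An on-time scan therefore always precedes the landmark. For a scan taken before Cycle 4 Day 1, only delays at the Cycle 2 and Cycle 3 starts can move it, and they must add up to more than about one to two weeks.

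Later nominal margins are 182.6 − 168 = 14.6 days (6 months), 273.9 − 252 = 21.9 days (9 months) and 365.2 − 336 = 29.2 days (12 months). A 28-day slip would exceed the first two, but there a late scan conceals only progressions since the previous scan. At 3 months it conceals every scan-detected progression since first dose.

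**Size at 3 months.** The documents give neither the share of late first scans (q) nor the share of progressions found only at scheduled scans (s); both are assumptions. Medians come from studies in Protocol Section 1.3: 2.7 months (lenalidomide alone, DLBCL), 3.7 months (all patients in the same study) and 6.2 months (lenalidomide alone, non-GCB). With exponential PFS, S(t) = 0.5^(t/median), and an on-time first scan at 84/30.4375 = 2.76 months:

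estimate = 1 − [(1 − s)(1 − S(3)) + s(1 − q)(1 − S(2.76))]

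For median 3.7: S(3) = 0.570 and S(2.76) = 0.596. With q = 0.2:
- s = 1: 1 − 0.8 × 0.404 = 0.677, which is 0.107 too high.
- s = 0.5: 1 − (0.5 × 0.430 + 0.5 × 0.8 × 0.404) = 0.624 after rounding, which is 0.054 too high.

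| Median (months) | True S(3) | q = 0, s = 1 | q = 0.2, s = 0.5 | q = 0.2, s = 1 |
|---|---|---|---|---|
| 2.7 | 0.463 | 0.492 | 0.528 | 0.594 |
| 3.7 | 0.570 | 0.596 | 0.624 | 0.677 |
| 6.2 | 0.715 | 0.735 | 0.751 | 0.788 |

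At median 3.7, q = 0.1 and q = 0.3 give 0.603 and 0.644 (s = 0.5), or 0.637 and 0.717 (s = 1).

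Part of the excess arises without any delay, because the scan precedes the landmark by 7.3 days. Lateness itself adds 0.677 − 0.596 = 0.081 when s = 1 and 0.624 − 0.583 = 0.041 when s = 0.5.

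**The case against.** - **Slippage is not certain.** Section 5.5.5 can also be read as letting the cycle clock run while lenalidomide starts late. This stands: the section supports both readings and has to be reconciled.
- **Progression can be found between scans.** Section 8.3.18 allows evaluation whenever indicated, subjects are examined often in early cycles, and deaths are dated without imaging. This stands, and is why s = 0.5 is shown. A reader might infer that 3-month PFS mostly measures scan timing; the documents do not support that.
- **The 57% figure is not a delay rate.** Section 1.9 reports that 57% of patients on lenalidomide monotherapy for mantle cell lymphoma had at least one dose interruption for an adverse event. It is tempting to use this as the rate of late scans. But it counts interruptions at any time, and under Section 5.5.5 a mid-cycle hold does not by itself move the next cycle's start. No document figure supports 20% or any other share.
- **DOR need not be overstated.** A late scan can postpone the recorded response as well as the recorded progression, so both ends move. Off treatment, subjects without documented progression are censored at the last assessment, which may be informative but has no known direction.
- **The effect is modest beside sampling error.** For 55 subjects and a rate of 0.57, the 95% half-width is 1.96 × √(0.57 × 0.43/55) = 0.13. That is fair, but this bias runs upward and does not average out.

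**Conclusion.** The concern holds as a modest weakness in secondary, descriptive endpoints. If delays move cycle starts, accumulated delay of more than about one to two weeks before Cycle 4 carries the first scan past 3 months and biases that PFS rate upward. With 20% of first scans late and a 3.7-month median, the excess is about 5 points if half of progressions are scan-detected and about 11 if all are. Both shares, the exponential form and the median are assumptions.

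Only the 3-month landmark is tight. The direction for DOR is not established. The passages on disease evaluation after stopping, and on the scan window, disagree and leave progression dating and censoring open to choice. The primary ORR test is not affected by this route.

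**What to change.** 1. **Anchor on-treatment scans to the calendar:** every 12 weeks ±7 days from first dose, whatever the dose delays. The planned interval is unchanged. The first scan would then fall at 77 to 91 days, always before 91.3. At a 3.7-month median with all progressions scan-detected, the 3-month estimate would be 0.571 to 0.623 against 0.570: some grid effect remains, but it no longer depends on toxicity. The cost is wording, and scans may no longer coincide with Day 1 visits.
2. **Reconcile the passages:** Sections 3.1 and 9.2 with Section 8.4.1 and Appendix 1 (footnote a) on evaluation after stopping; Section 7.3.1 with Appendix 1 (footnote n) on the scan window; and the two statements in Section 5.5.5 on whether the cycle clock moves. It would be tempting to call this free of added scans, but Section 3.1 never names imaging, so requiring it after stopping could add some.
3. **If scans stay cycle-anchored,** report a 4-month PFS landmark (4 × 30.4375 = 121.8 days, which covers 84 + 28 + 7 = 119) in place of or beside 3 months, and add an interval-censored sensitivity analysis for scan timing. The SAP times are given only as examples, so this is a wording change. The 6-, 9- and 12-month landmarks need not move. SAP Section 6 says results had already been presented, so for scans already taken this third item is the one still available.

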7.3.2. Physical Examination

Physical examination findings should be used at the time of response evaluation to assess both response and/or progression. Abdominal examination to assess for enlarged liver and/or spleen should be performed and documented, with verification of findings by radiographic imaging preferred. Non-palpable liver and spleen is required for CR response category.

Any new or enlarged palpable masses suspected to be disease progression should be verified by radiographic imaging when possible.

7.3.3. Bone Marrow Aspirate and Biopsy

A unilateral bone marrow aspirate and biopsy will be done at Screening or up to 28 days before the first dose of study drug.

For Phase 1b: Follow-up bone marrow aspirate and biopsy will only be required to confirm CR if result was positive at Screening.

For Phase 2: If the baseline PET result is positive for bone marrow involvement, a baseline bone marrow aspirate and biopsy is no longer required ([Cheson 2014](#)). [For clinical trial purposes and to ensure eligibility, baseline bone marrow samples/results will be collected.]

For CR in Phase 2:

If the PET result is positive for bone marrow involvement at baseline and confirmed negative at CR, a follow-up bone marrow aspirate and biopsy is not required to confirm CR; if the PET result is negative at baseline and the bone marrow aspirate and biopsy (which is then required at baseline) is positive at baseline, a confirmatory follow-up bone marrow aspirate and biopsy to confirm CR is required ([Cheson 2014](#)).

Subjects who have a bone marrow aspirate and biopsy result since completion of their last therapy for DLBCL may use those bone marrow results in lieu of the baseline bone marrow aspirate and biopsy required for this study provided the biopsy and aspirate were done within 28 days of first dose of study drug.

Additional samples may be collected for biomarkers and other exploratory evaluations.

7.4. Survival and Subsequent Anticancer Therapies

7.4.1. Survival

After disease progression or study treatment discontinuation, subjects will be contacted to assess survival status every 12 weeks (± 14 days) from End-of-Treatment Visit until death, subject withdrawal of full consent, lost to follow-up, or study completion, whichever comes first. At the time of the analysis and at study completion, a survival sweep will be conducted. All subjects who are not known to have died or withdrawn consent prior to survival sweep will be contacted at that time.

7.4.2. Subsequent Anticancer Therapies

After study treatment is complete, the following information on subsequent anticancer therapies will be collected every 12 weeks (± 14 days) from End-of-Treatment Visit to death, subject withdrawal of full consent, loss to follow-up, or study completion, whichever comes first:

- Receipt of subsequent anticancer therapies
- Indication for subsequent anticancer therapies

7.5. Clinical Laboratory Assessments

7.5.1. Hematology

Hematology parameters will include a complete blood count: white blood cells, red blood cells, hemoglobin, hematocrit, platelets, neutrophils, lymphocytes, monocytes, eosinophils, basophils and bands (if reported). See time points specified in the Schedule of Assessments ([Appendix 1](#)).

